4.1.4. Extent of Exposure

The treatment duration is defined as date/time of last study drug intake – date/time of first study drug intake + 72 hours.

Note: treatment interruptions will not be taken into account for the above definition.

Actual treatment duration will be summarized descriptively by treatment group.

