- e. Day 28 assessments include only the assessments indicated. Other safety assessments need only be collected if deemed clinically necessary based on an assessment of the subject's safety or as follow-up to an earlier AE.
- f. Procedures performed as part of standard of care within approximately 48 hours prior to screening completion (ie, randomization) may be used in determining study eligibility.
- g. These assessments are not required per protocol, however, if clinical/safety evaluations are performed as part of routine clinical care while hospitalized, the results of these assessments will be collected in the eCRF for viral, safety, and/or clinical evaluation.
- h. Study drug should be given as soon as possible but no later than 4 hours after randomization. Study drug will be given as an LD administered for Dose 1 followed by 9 MDs, to be given at least 8 hours apart and maximum 16 hours apart, with no more than 2 doses per calendar day, for a total of 10 doses over 5 or 6 days. ALS-008176 may be given without regard to food. The date and time of dose administration, the date and time of food intake (limited to the food ingested within 30 minutes before or after study drug administration), and the type of food will be recorded in the eCRF during hospitalization. The date and time of dose administration will be recorded in the electronic device used for eCOA in case the subject is discharged prior to completion of treatment. See [Attachment 8](#) for details on collection of food intake information.
- i. Upon discharge, subjects will be required to document intake of study drug on the electronic device used for eCOA in a study drug log.

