Given the active nature of the ongoing development program, the IDMC may recommend that one of the dose regimens be removed or one or both of the dose regimens be adjusted based on safety and/or antiviral activity considerations from ongoing studies. Irrespective of the dose, the average projected ALS-008112 plasma exposure ([Table 5](#)) will not exceed a projected average AUC_{0-24h} of 20,000 ng.h/mL, a limit that is 2.5-fold lower than the lowest systemic NOAEL observed in nonclinical toxicity studies.

Treatment Duration

Treatment will last for 5 days as this was the duration of treatment assessed in healthy adult subjects infected with RSV in a human challenge model (Study ALS-8176-502), which demonstrated substantial declines in RSV RNA viral load and improvement in RSV signs and symptoms. The long terminal $t_{1/2}$ of the NTP is anticipated to provide therapeutic levels of the

active NTP beyond the 5-day dose duration. The treatment duration may be extended to up to 10 days if recommended by the IDMC, based on emerging data from the present and other ongoing clinical studies with ALS-008176.

Clinical Outcomes of RSV Treatment

Treatment with ALS-008176 may reduce the severity and duration of RSV signs and symptoms and their impact on functioning, reduce the need for and duration of supportive care (eg, oxygen supplementation, IV fluids, days of hospitalization) and accelerate the subjects' return to pre-RSV health status and HRQoL. The study will compare treatment regimens to evaluate the impact of treatment with ALS-008176 on the clinical course of RSV disease.

Biomarker Collection

Blood samples will be collected for exploratory biomarker analyses (host RNA), on the premise that these markers may play a role in the treatment response, PK, safety of ALS-008176, or the status and change of the RSV-related disease. In addition, leftover mid-turbinate nasal swabs or blood samples collected for other testing may be used for biomarker analysis (eg, proteins including cytokines) if available on the same premise. They may help to explain interindividual variability in clinical outcomes or to identify population subgroups that respond differently to the drug.

Biomarker samples may be used to help address emerging issues and to enable the development of safer, more effective, and ultimately individualized therapies.

Biomarker analyses may be performed upon the discretion of the sponsor and will be reported separately from this study.

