The study drug ALS-008176 will be provided as tablets for oral administration. Study drug administration should start as soon as possible, but no later than 4 hours after randomization in order to maximize the opportunity for the compound to inhibit viral replication and potentially improve outcomes. Subjects will be dosed with a single oral LD followed by 9 MDs twice daily (at least 8 hours apart) during Day 1 to Day 5/6 (depending on the timing of the LD). Administration of the doses should occur at approximately the same time each day after the collection of the mid-turbinate nasal swabs.

Assessments during the study will include the antiviral activity, measured by mid-turbinate nasal RSV RNA viral load using a qRT-PCR assay as well as an evaluation of the clinical course of RSV infection as assessed by the clinician and an evaluation of RSV disease-related signs and symptoms and HRQoL as assessed by the subject.

Safety and tolerability, including AEs, laboratory assessments, ECGs, physical examination, and vital signs will be assessed throughout the study from signing of the informed consent form (ICF) until the subject's last study-related activity.

Pharmacokinetic assessments during the study will be based on sparse sampling and will be performed using a population PK (popPK) model.

Sequence analysis will be performed to identify pre-existing sequence polymorphisms, to characterize RSV variants of the L-gene and other regions of the RSV genome if warranted, and to evaluate emergence of any resistance-associated mutations. Additionally, exploratory

biomarkers (derived from blood biomarker samples, leftover mid-turbinate nasal specimens, or leftover blood samples) may be assessed to determine the effects of ALS-008176 on markers of RSV disease.

An unblinded IDMC will be commissioned for this study and a Sponsor Committee will be established. Based on the recommendations of the IDMC following interim analyses/reviews of PK, efficacy, and safety data, changes to enrollment in the treatment arms, dose regimen adjustments, or an increase in dose duration to 10 days may be implemented. A maximum of 2 interim analyses are planned to assess the primary endpoint for early superiority and futility. The first interim analysis will be performed when at least 45 subjects have been randomized, preferably after the end of a hemispheric RSV season. If the study is considered underpowered, a sample size increase may be suggested to a maximum of 180 subjects.

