For the analyses per time point in order to have only one evaluation per subject per analysis time point, the following rules will be applied:			
In case multiple nasal swabs were taken on a single day, the average on the log scale will be used as the value for that subject. For other assessments, if there are two measurements on the same date and/or time, then the measurement with the highest sequence number will be used.			
If two assessments on different days fall within the same interval, the measurement closest to the target day will be used. If they are equidistant, the last measurement within the interval will be used.			

The baseline record (day 1) is defined as the last record before the first intake of the study drug. For RSV RNA viral load, in case a result is available that is no later than 1 hour after treatment initiation this may be used, but only if no pre-treatment observation is available.

On-treatment is defined as the period from the first medication intake until last medication intake + 72 hours (i.e. Treatment Phase).

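### SAP 4.1.4 reports the analysis Treatment phase, with its 72-hour tail, as actual treatment duration: at 12-hour spacing a 10-dose course reads 7.5 days against a first-to-last-dose span of 4.5

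*SAP*

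**What the plan says.** SAP 4.1.4, under Extent of Exposure, takes the time of last intake, subtracts the time of first intake and adds 72 hours; the formula ends "date/time of first study drug intake + 72 hours". A note says that "treatment interruptions will not be taken into account for the above definition". The section then says: "Actual treatment duration will be summarized descriptively by treatment group". No other duration is defined there, so the quantity called actual must be the one with the 72 hours in it.

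The same 72 hours appear in SAP 2.1, where they end the Treatment phase and set the on-treatment window: "On-treatment is defined as the period from the first medication intake until last medication intake + 72 hours".

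On the length of dosing itself:

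- Protocol 3.2 (Treatment Duration): "Treatment will last for 5 days as this was the duration of treatment assessed in healthy adult subjects".
- Protocol Time and Events Schedule, footnote h: doses are "to be given at least 8 hours apart and maximum 16 hours apart, with no more than 2 doses per calendar day". The same footnote spreads the full ten-dose course across five or six days.
- SAP 1.2: one loading dose and nine maintenance doses twice daily, in a treatment phase that runs from Day 1 to Day 5/6.

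**The concern.** A window for allocating events to phases and a measure of exposure serve different purposes. The first reasonably runs past the last dose. The second should say how long subjects were dosed. SAP 4.1.4 uses the first as the second, and the SAP defines no time-based measure of dosing without the tail.

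At stake is one descriptive table. Its absolute values would not match the course length that the protocol describes. The protocol also allows dosing to be extended to up to 10 days, so a reader of the report would not necessarily recognise 7.5 days as a completed standard course. A subject who stopped after one dose would be listed with three days of treatment.

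**Working it through.** **Inputs.** Ten doses, hence nine intervals (SAP 1.2). Twice-daily dosing, taken as 12 h nominal. Permitted interval 8 to 16 h, at most two doses per calendar day (Protocol, footnote h). Added constant 72 h (SAP 4.1.4).

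**Step 1: reproduce the documents' own description.** First-to-last span = 9 × 12 h = 108 h = 4.5 days. A loading dose at 08:00 on Day 1 puts dose 10 at 20:00 on Day 5. One at 20:00 puts it at 08:00 on Day 6. This agrees with Day 5/6 and with ten doses over 5 or 6 days.

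**Step 2: apply the SAP formula.** 108 + 72 = 180 h = 7.5 days, which is 180/108 = 1.67 times the span. The constant makes up 72/180 = 40% of the reported value. With an 08:00 loading dose the reported duration runs to 20:00 on Day 8.

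**Step 3: partial courses at 12 h spacing.** Span = (doses − 1) × 12 h.

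| Doses taken | Last − first | Share of full course | SAP 4.1.4 | Share of full course |
|---|---|---|---|---|
| 1 | 0 h | 0% | 72 h (3.0 d) | 40% |
| 5 | 48 h | 44% | 120 h (5.0 d) | 67% |
| 10 | 108 h | 100% | 180 h (7.5 d) | 100% |

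**Step 4: permitted range for a full course.** On an hourly grid, with 8 to 16 h intervals and no more than two doses per calendar day, the span runs from 89 h to 144 h (3.7 to 6.0 days). Requiring dose 10 to fall by the end of Day 6 changes the upper end only to 143 h. Adding 72 h gives 161 h to 216 h (6.7 to 9.0 days).

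**Step 5: what a constant does and does not change.** Ten doses against one: 180 − 72 = 108 h, the same as 108 − 0. Differences between subjects, differences between arms in mean or median, and the SD are all unchanged. Of the statistics that SAP 2.4 lists for continuous variables, the mean, median, minimum and maximum each rise by 72 h.

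**The case against.** The formula matches the SAP's own framework. SAP 2.1 ends the Treatment phase 72 h after the last intake, and 4.1.4 gives the length of that phase. A reader might infer a copying slip or an arithmetic error, but nothing in the documents shows one. The formula is disclosed, and the tail can be subtracted.

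A reader might also infer that the tail narrows the gap between completers and early stoppers, or conceals early stopping. Step 5 rules out the first: only ratios move, and the SAP plans no ratios for this variable. The second overlooks other planned output. SAP 4.1.2 tabulates treatment discontinuations with reasons, 4.1.3 summarises compliance by arm, and 4.3.1 summarises and lists adverse events leading to permanent stop.

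Time after the last dose is also not pharmacologically empty. Protocol 3.2 gives half-lives for the active triphosphate of 17.6 h (cell culture) and about 29 h (monkey lung), and expects therapeutic levels to outlast dosing. By those figures 72 h is 72/29 = 2.5 to 72/17.6 = 4.1 half-lives. But 4.1.4 does not offer this reason, and a period of persisting drug effect would still not be actual treatment duration.

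Finally, 4.5 days is stated nowhere in the documents. It assumes exact 12 h spacing, and last minus first gives zero for a subject who took one dose, so some additive convention is defensible. That stands. It argues for a stated dosing-interval convention, not for 72 h.

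**Conclusion.** The point holds as one of definition and labelling. SAP 4.1.4 reports the length of the analysis Treatment phase as actual treatment duration. A standard course then reads 7.5 days at 12 h spacing (6.7 to 9.0 days over the permitted intervals), against a dosing span of 4.5 days (3.7 to 6.0). At nominal spacing that exceeds the 5 days, or Day 1 to Day 5/6, that the documents give. One dose reads as 3 days, or 40% of a full course.

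The effect is confined to absolute values and proportions in descriptive exposure output. Between-arm differences and SDs are unchanged, early stopping remains visible elsewhere, and the primary test, its alpha and its power are untouched. The priority is low.

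The point figures rest on exact 12 h spacing and the 10-dose regimen. The 72 h offset itself rests on neither.

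**What to change.** In SAP 4.1.4:

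1. Define dosing duration as last intake minus first intake. If one dosing interval is added so that a single dose does not count as zero, say so. With 12 h added, ten doses give 108 + 12 = 120 h (5.0 days, in line with Protocol 3.2) and one dose gives 12 h, or 10% of that.
2. Summarise the number of doses taken beside it. The compliance measure in 4.1.3 counts tablets against a planned 12, and the loading dose is three tablets, so one dose of ten appears there as 3/12 = 25%. It does not stand in for a dose count.
3. Keep the 72 h for the Treatment phase and on-treatment windows in SAP 2.1. If that length is also reported, label it *treatment phase duration*.

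The cost is SAP wording and the matching table specification. Protocol section 6 already has the date and time of each dose recorded, in the eCRF during hospitalisation and in the electronic device after discharge, so no new data are needed.

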4.1.5. Protocol Deviations

Only major protocol deviations will be defined in this trial. All major protocol deviations will be listed, including the deviations to the inclusion-exclusion criteria, and the violations to the prohibitions and restrictions, if any.

Note that the Per-protocol set definition takes into account any deviation from the protocol that could affect the efficacy. These are not necessarily major deviations, nor are major deviations considered to always affect efficacy and to warrant exclusion from the PP analysis.

4.1.6. Medical History

The medical history records will be listed; separate listings will be generated for conditions of interest (allergic/immunologic, dermatological)

4.1.7. Preplanned Surgeries/Procedures

Preplanned surgeries and procedures will be listed.

4.1.8. Prior and Concomitant Medications

Medications taken 14 days before the Screening Visit and up to the Safety Follow-up Visit will be summarized by preferred term using the World Health Organization-Drug Dictionary for the ITT-i Set as frequency tables in 2 parts:

1. Prior medication: medication that started before the first dose of study drug, regardless of when dosing of the medication ended
2. Concomitant medication: medication received at or after the first dose of study drug, medication that was received before initial dosing and continued after initial dosing of study drug, or medication with missing stop date.

(Medication that started before the first dose of study drug and continued after the first dose of study drug will be summarized as prior medication and separately as concomitant medication.)

The part on concomitant medication will be shown by ATC class level up to level 3.

If a prior/concomitant therapy record misses components of its start and/or stop dates (time and/or day and/or month and/or year), the following actions will be taken:

1. In case of partial start or stop datetimes, the concomitant therapy records will be allocated to prior/concomitant using the available partial information, without imputations.
2. In case of a completely missing start date, the prior/concomitant therapy will be considered as having started before the trial.
3. In case of a completely missing end date, the prior/concomitant therapy will be considered as ongoing at the end of the trial.

Separate tables will be made for medication related to fever and not related to fever. Medication related to fever will be categorized as Acetaminophen/paracetamol, Ibuprofen, or other.

4.2. EFFICACY

The efficacy analyses include the following primary, secondary and exploratory endpoints.

Primary endpoint

- RSV RNA \log_{10} viral load (measured by qRT-PCR in the mid-turbinate nasal swab specimens) AUC from immediately prior to first dose of study drug (baseline) until Day 7 (or up to 11 days if the dose duration is extended to up to 10 days).

Secondary endpoints

- RSV clinical course endpoints:
 - Length of hospital stay from admission to discharge and from study treatment initiation to discharge.
 - Length of hospital stay from admission to readiness for discharge and from study treatment initiation to readiness for discharge, with readiness for discharge defined by the investigator.
 - Need for and duration of intensive care unit (ICU) stay.
 - Need for and duration of supplemental oxygen (regardless of method used).
 - Number of hours until peripheral capillary oxygen saturation (SpO₂) $\geq 93\%$ on room air among subjects who were not on supplemental oxygen prior to current hospitalization.
 - Respiratory rate, SpO₂, and body temperature return to pre-RSV disease level.
 - Need for and duration of noninvasive ventilator support (eg, continuous positive airway pressure) and/or invasive ventilator support (eg, endotracheal-mechanical ventilation or mechanical ventilation via tracheostomy).
 - Time to return to pre-RSV functional status (Katz ADL score).
 - Need for hydration and feeding by IV catheter/enteral tube.
 - Time to clinical stability defined as the time at which the following criteria are all met:
 - normalization of blood oxygen level (return to baseline; by pulse oximetry) without requirement of supplemental oxygen beyond baseline level
 - normalization of oral feeding
 - normalization of respiratory rate
 - normalization of heart rate

- Improvement on the ordinal scale
- All-cause mortality.
- RSV RNA viral load as measured by qRT-PCR of the mid-turbinate nasal swab specimens which will be used to determine the following:
 - Viral load over time.
 - Peak viral load, time to peak viral load, rate of decline of viral load, and time to RSV RNA viral load being undetectable.
 - Proportion of subjects with undetectable viral load at each time point.
 - RSV RNA viral load AUC from immediately prior to first dose of study drug (baseline) until Day 10 and until Day 14.

Exploratory endpoints

- The amount of:
 - Supplemental oxygen above pre-RSV disease level (regardless of method used) from study treatment initiation to Day 7.
 - Oxygen delivered by noninvasive ventilator support (eg, continuous positive airway pressure) and/or invasive ventilator support (eg, endotracheal-mechanical ventilation or mechanical ventilation via tracheostomy).
 - Subjects (proportion) who started antibiotic use after the first dose of the study drug.
- Disease status and presence of complications with onset after treatment initiation:
 - Bacterial superinfections reported as AEs (eg, pneumonia, acute otitis media, sinusitis, bronchitis, bacteremia).
 - Exacerbations of underlying pulmonary disease (eg, asthma, chronic obstructive pulmonary disease).
 - Cardiovascular and cerebrovascular events (eg, myocardial infarction, congestive heart failure exacerbation, arrhythmia, stroke).
 - Respiratory failure
 - *Clostridium difficile* associated diarrhea
 - Other

- Duration and severity of signs and symptoms of RSV infection as assessed by the respiratory infection patient-reported outcome (RI-PRO) questionnaire and additional questions about health and functioning completed by the subject in the eCOA.
- HRQoL assessed by the EuroQoL 5 Dimension visual analogue scale (EQ-5D VAS) completed by the subject in the eCOA.
- Hospital readmission for respiratory reasons up to the Day 28 follow-up visit.
- RSV RNA viral load (AUC) as measured by qRT-PCR of endotracheal samples in intubated subjects.
- Lung function measured by the DLCO and spirometry test.
- RSV infectious viral load as measured using a quantitative viral culture (plaque assay).

